This study is an open-label, randomized controlled trial. Patients will be randomized into two groups of 15, "Routine Care" group, which will serve as the control group, and "Octreotide" group. The amount of bronchial secretions is routinely measured in all mechanically ventilated patients. Once the Primary Team identifies a patient as a candidate for the study, the study team will review their medical records and assess the patient based on the inclusion and exclusion criteria to determine if they are qualified to participate in the study (screening). If the patient is qualified, one of the study members will explain the research project to the patient or his/her authorized representative and also explain the informed consent process. This study does not compensate patients for participating in the study or for any potential injuries/illness arising out of their participation in this study. This aspect will be made clear to the patients (or their authorized representative) in addition to other risks and benefits of participation in this study. If the patient or his/her authorized representative agrees to participate in the study informed consent will be obtained. After informed consent, the patient will be administered

standard of care medications for the first 24 hours after the screening and a baseline volume of bronchial secretions during this 24 hour period will be recorded. Additionally, medications administered and procedures performed during this 24 hour period would also be recorded. Then, a security envelope containing group assignment will be opened by the ICU attending physician. Both groups will continue to receive treatments that have already been initiated to manage bronchial secretions. In addition, "Octreotide" group will receive parenteral octreotide, while "Routine Care" group will not receive any additional treatment for the study. All patients will continue to receive the care deemed necessary by the ICU attending physician and his/her team. These interventions will be continued for 72 hours or until extubation or withdrawal from the study, whichever occurs earlier. Subsequently, the standard of care management, as determined by the Primary Team, will be continued.

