Baseline volume of bronchial secretions suctioned over a 24-hour period will be recorded for all subjects, and interventions prescribed by the random treatment assignment will be initiated and continued for up to 72 hours. Simultaneously, the rate of secretions will be measured and recorded (by registered nurses taking care of the patients) during each 24-hour shift. Volume of normal saline used to flush endotracheal tube will be recorded and then subtracted from the total volume found in the suction container in the end of each shift. Effectiveness of the interventions studied in this trial will be determined by comparing the percent change in the secretions rate (relative to the baseline rate) between the “Octreotide” and “Routine group” subjects, which will be the primary outcome. The secondary outcome will be the percentage of patients who were extubated within 72 hours after initiating the interventions (“Octreotide” vs “Routine”).

Assessment of Safety:

The study will be performed in mechanically ventilated patients in an ICU, an environment where close monitoring of all patients in an absolute requirement. Similarly to the patients in the control arm, subjects in the treatment arm will be closely monitored for adverse reactions of octreotide. Close monitoring includes continuous and periodic monitoring of vital signs including Heart Rate, Blood Pressure and Respiratory Rate. Based on these data, as well as results of serum chemistry performed at least daily (which is part of the standard care in ICU), doses of beta-blockers, calcium channel blockers, insulin, and agents to control fluid and electrolyte balance will be adjusted, - similarly to situations when octreotide is used for other medical conditions.

Given the reported adverse reactions of octreotide, an electrocardiogram will reviewed for each subject, and patients with bradycardia and significant conduction defects will be excluded (see the exclusion criteria). During the study, vital signs will be monitored every hour, and cardiac activity will be continuously monitored by telemetry. To confirm timely assessment of safety,

the study team will ensure that the vital signs data are recorded every 4 hours in the data collection tool.

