If a patient develops bradycardia (HR < 60 bpm), octreotide administration will be stopped and the patient will be withdrawn from the study. Furthermore, if a subject experiences increase in systolic BP to 180 mmHg or above, octreotide administration will be stopped and the patient will be withdrawn from the study. However, if a subject experiences increase in systolic BP by at least 40mmHg over 2 hours, the infusion rate will be decreased to 12 mcg/hr; the BP will be reassessed every hour, and the infusion rate will be titrated up as tolerated to a maximum of 25mcg. Given octreotide's effect on serum glucose level, all subject's capillary blood glucose (CBG) will be monitored every 4 hours to monitor for hyperglycemia and hypoglycemia. The glucose levels every 4 hours will be recorded in the data collection form. Subjects who are hyperglycemic and require more than 20 units of intravenous insulin per hour will be withdrawn from the study, as will subjects who experience hypoglycemia (CBG < 60 mg/dL) despite being on 5% dextrose drip.

Statistical analysis:

Data will be analyzed with the assistance of a statistician at Danbury Hospital's Department of Research and Innovation. The differences between the two groups (Routine Care vs. Octreotide) in the percentage change of rate of secretion (defined as milliliters per 24 hours) for each of the 24-hour periods as compared to the baseline 24-hour period and proportion of patients extubated within 72 hours (defined as both time to extubation AND yes/no extubated within 72 hours) will be compared. The Fisher's exact test will be used to assess statistical significance (alpha set at $p < 0.05$). If the sample size allows and there are adequate cell frequencies, regression analyses will be used to assess the association between the use of Octreotide and the primary outcome variables.

Given that no previous research has been conducted to examine management of bronchorrhoea resistant to conventional interventions in mechanically ventilated patients, a power calculation to estimate the sample size cannot be performed reliably. We do recognize the small sample size to be included in our study and intend for this project to serve as a pilot study that would provide some evidence-based information to guide clinicians at our institution in such situations and provide background information for further studies on a much larger scale.

References:

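### The only significance test named, Fisher's exact test, cannot be run on the continuous primary outcome without a choice the plan does not contain

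*Combined protocol and SAP*

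**What the plan says.** Assessment of Efficacy judges effectiveness by "comparing the percent change in the secretions rate (relative to the baseline rate) between the" two arms and makes this the primary outcome. The secondary outcome is the percentage extubated within 72 hours of starting the interventions.

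Statistical analysis expresses the primary outcome in millilitres per 24 hours, "for each of the 24-hour periods as compared to the baseline 24-hour period". It lists the extubation proportion beside it, "defined as both time to extubation AND yes/no extubated within 72 hours". The next sentence is the only one that names a significance test: "Fisher's exact test will be used to assess statistical significance", with alpha 0.05. One further method follows: "If the sample size allows and there are adequate cell frequencies, regression analyses will be used" for the primary outcome variables. No model type, covariates or handling of repeated periods is given.

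Trial Design gives 15 patients per arm and the sentence "This study is an open-label, randomized controlled trial". On duration it says: "These interventions will be continued for 72 hours or until extubation or withdrawal from the study, whichever occurs earlier".

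**The concern.** Fisher's exact test compares counts in categories. A percent change in mL/24 h is a measurement, and the documents contain no responder definition or threshold that would turn it into categories. Nor do they name a t-test, rank test, covariance analysis, mixed model or log-rank test. The stated rule therefore yields no p-value for the primary outcome until someone adds a cut-point or substitutes another test. Nothing in the plan requires that choice to be made before the results by arm are known.

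Two related gaps sit in the same paragraph. Each 24-hour period is to be compared and none is named primary, so a better test alone would still leave up to three primary tests. Also, one label covers both time to extubation and extubation yes/no, and Fisher's test suits only the second.

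**Working it through.** **Inputs.** From the documents: 15 per arm; alpha 0.05; up to three 24-hour periods in 72 hours. Assumed: two-sided testing (sidedness is not stated), normal data with equal SDs for power, effects of 1.0 and 0.8 SD, and between-period correlations of 0 to 0.9. The documents give no SD, effect or power figure, so there is no stated figure to reproduce.

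**1. Fisher's test on the uncategorised outcome.** With 30 distinct values the table is 2 × 30. All C(30,15) = 155,117,520 allocations are then equally likely given the margins, so p = 1 whatever the data. A cut-point is needed.

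**2. Size once there is a cut.**
- Cut fixed in advance: size = Σ Bin(a; 15, π) Bin(b; 15, π) over all tables (a, b) with Fisher p < 0.05. This gives 0.5% at π = 0.1, 1.7% at π = 0.3 and 1.7% at π = 0.5. The maximum over π is 1.8%.
- Split at the pooled median: the test rejects when 11 or more, or 4 or fewer, of one arm fall below the median. Size = 2 × [C(15,11)² + C(15,12)² + C(15,13)² + C(15,14)² + C(15,15)²] / C(30,15) = 2 × (1,863,225 + 207,025 + 11,025 + 225 + 1) / 155,117,520 = 2.7%.

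Both are below 5%, so a single cut does not inflate error.

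**3. Power.**
- t-test: noncentrality = d√(n/2). At d = 1.0 this is √7.5 = 2.739, with 28 df and critical value 2.048.
- Fisher, fixed cut midway between the arm means: event probabilities are Φ(−d/2) and Φ(d/2). At d = 1.0 these are 0.309 and 0.691, entered in the exact sum of step 2.
- Rank-sum and Fisher after a median split: by simulation.

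| Method | 1.0 SD | 0.8 SD |
|---|---|---|
| t-test | 75% | 56% |
| Rank-sum | 72% | 52% |
| Fisher, median split | 48% | 31% |
| Fisher, midway cut | 39% | 25% |

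For 80% power the t-test needs an effect of about 1.06 SD; Fisher at the midway cut needs about 1.54 SD.

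**4. Replacement test chosen after seeing the data (no true effect, simulated).** Taking the better of t-test and rank-sum gives 5.7% (normal data) to 6.0% (lognormal). Adding a median-split Fisher test gives 6.5% to 6.8%.

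**5. Test replaced, three periods kept.** One exact rank-sum test at 15 per arm has size 4.5%. With three independent periods, the chance of at least one false positive is 1 − (1 − 0.045)³ = 12.9%. Simulation gives 13.0% at correlation 0, 11.7% at 0.5 and 8.1% at 0.9.

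**The case against.** The strongest reply concerns how the paragraph is read. The Fisher sentence follows directly on the extubation proportion, for which the test is right, and the regression sentence refers to the primary outcome variables. One can fairly read Fisher's test as meant for the proportion and regression as meant for secretions. The text does not settle this. On that reading the fault is an under-specified analysis rather than a wrong test, but the primary outcome still has no defined analysis.

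A reader might also infer that the cell-frequency condition is meaningless for a continuous outcome. That goes too far: cell counts can matter for categorical predictors in a linear model, and the plural wording may include extubation yes/no. What stands is that the condition is undefined.

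A reader might further infer serious inflation of false positives, for instance from trying many cut-points. The plan proposes no such search. A cut fixed in advance gives no inflation, and a late choice among ordinary tests adds only one to two percentage points. The 8% to 13% arises from having no primary period and would remain with a suitable test.

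The open-label design adds little, because any test chosen once allocation is known raises the same problem. The planned help of a statistician is useful but fixes nothing in advance. Pilot status explains the absent power calculation and makes lost power less serious. It does not remove the mismatch, because a test at 0.05 is still planned and the results are meant to inform clinicians at the institution.

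**Conclusion.** The point holds. On either reading the plan gives no usable test for its primary outcome: Fisher's test lacks categories, or an untyped regression depends on an undefined condition. This follows from the text and needs no numerical assumption.

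The main cost of forcing Fisher's test with a fixed cut is power, at about 39% against 72% to 75% for the continuous-data tests at 1.0 SD. Those figures rest on assumed effects and normal data. The false-positive cost of choosing a test late is modest, about 6% to 7%. If three periods are each tested with none named primary, the chance of at least one false positive is about 8% to 13%, depending on an assumed correlation. The documents do not support a claim that the plan as written produces gross false-positive inflation, nor a claim that Fisher's test is wrong for extubation yes/no.

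**What to change.** 1. Limit Fisher's exact test to extubated yes/no within 72 hours.
2. Before any comparison by arm, name one primary secretion summary and one test for continuous data at 0.05. Examples are a rank-sum test on percent change, with the Hodges-Lehmann difference and 95% CI, or a baseline-adjusted linear model on the rate. Only one should be primary.
3. Report the separate 24-hour periods as supportive, with estimates and CIs.
4. Remove the sample-size and cell-frequency condition for this outcome.
5. Treat time to extubation as a separate outcome and, if it is kept, use a time-to-event method.

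The summary should include patients extubated before 72 hours. A rate over intubated time is one option, with two limits to state. It compares windows of different length and can understate a delayed effect. It also needs part-period net volumes and extubation times.

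A responder cut-point fixed in advance would also cure the mismatch, at the power cost shown.

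**Cost.** One paragraph of text, and possibly recording volume and time at extubation. The plan says that "The amount of bronchial secretions is routinely measured in all mechanically ventilated patients", but it should not be assumed that no new recording is needed. The chart-review list does not name secretion or saline-flush volumes. The measurement interval also differs between Trial Design (twice daily) and Assessment of Efficacy (24-hour shifts).
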